If so, which are changed and in what way					X	X	X	X
FIHOA hand function score	X				X	X	X	X
If has lung disease (COPD, asthma etc)	X							
If has diabetes	X							

If has cardiovascular disease	X				
If has arthritis (e.g RA)	X				
If has balance problems (e.g. due to neurological disease such as PD)	X				
Free text medical information	X		X	X	X
Level of exercise (defined in category of minutes)	X		X	X	X
Level of activity in daily living (defined in cat of min)	X		X	X	X
If afraid to get hurt during physical activity / exercise (kinesiophobia)	X		X	X	X
30 second chair stand test		X	X	X	X
Specific joint pain (0-10 NRS)	X	X	X	X	X
Overall health (0-10 NRS)	X	X	X	X	X
EQ5D-5L	X		X	X	X
Educational level	X				
Work situation	X		X	X	X
Patient acceptable symptom state	X		X	X	X
If considers treatment failed			X	X	X
Motivation - ready to start exercising (0-10)	X				

FIHOA: Functional index for hand osteoarthritis patients. COPD: Chronic obstructive pulmonary disease, RA: Reumatoid Arthritis, PD: Parkinson's Disease, NRS: Numeric Rating Scale

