The overall aim of this project is to evaluate changes in health outcomes during participation in the digitally delivered treatment programme Joint Academy® (JA) containing exercise and education for patients with osteoarthritis (OA) of the hand.

Specific research questions are:

(1) What are the short-term changes in health outcomes of digitally delivered treatment for OA of the hand? Primary outcome is to examine pain and perceived hand function in participants following 3 months of digitally delivered first-line treatment for hand OA

Main exposures and outcomes

All participants answer patient- and disease relevant socio-demographic and outcome questionnaires at baseline and every third month during treatment. Additionally, participants report pain every week.

Pain will be assessed using the Numerical Rating Scale (NRS, discrete boxes 0–10) with the instruction: “Mark on this scale how much pain you had the last week in your hand”, followed by a 0–10 scale where 0 was defined as *No pain* and 10 was defined as *Maximum pain* (25).

To evaluate hand function, the Functional Index for Hand OsteoArthritis (FIHOA) will be distributed. The FIHOA is a 10-item questionnaire based on a semi-quantitative assessment scoring the disease on a 4-point scale. The FIHOA has been shown to be valid, sensitive, clinically relevant for the population and shown consistency and acceptable reliability (26). The literature also suggests it is associated with pain, muscle strength and health related quality of life in people with hand OA (27).

Among other outcomes to be reported are health-related quality of life assessed with the EuroQol – 5 dimension descriptive system (EQ-5D-5L), work situation, medication use (dichotomous reply, yes/no), changes in medications, willingness for surgery (dichotomous reply, yes/no), physical activity, exercise, fear of physical activity (yes/no) and motivation to start exercising using a Numerical Rating Scale (NRS, discrete boxes 0–10).

All outcomes will be self-assessed and self-entered using the digital program interface. Demographic and socioeconomic data and data on the participants’ overall health and characteristics (e. g age, gender, educational level BMI) will be collected at inclusion. The exposure and outcome measures are described in Table 1.

The digital program Joint Academy®

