In an attempt to scale and improve implementation of evidence-based guideline-derived first-line treatment for a number of musculoskeletal conditions (education and exercise), the digital self-management and education program Joint Academy® (JA) was developed in Sweden. The first JA program was developed in 2014 for persons with hip- and knee OA (28). The program for hand OA is available for patients since late 2021. The program is part of the health-care system in Sweden.

Participants join the programme through recommendation by their local physiotherapist (PT), occupational therapist (OT) or orthopaedic surgeon, via online advertisements and campaigns placed on search engines and social networks, or through their insurance company. A majority of included participants had a clinical diagnosis of hand arthritis from a PT, OT or physician, and all had a physical visit with a healthcare provider regarding their hand OA prior to joining JA. The clinical diagnosis of OA was confirmed by a PT or OT via telephone, or if deemed necessary the patient was recommended to seek face-to-face care before inclusion in the programme.

The Joint Academy® (www.jointacademy.com) program for people with hand OA consists of video instructed and progressively adaptable daily exercises, patient education through text lessons, possibility for a social chat group with other patients and a continuous asynchronous chat function with a personal reg. physiotherapist who supervises the patient during the full participation period. The program also contains three telephone consultations with a physiotherapist that were compulsory, one at the start, one after six weeks and one after three months. The intervention procedure is similar to that for hip and knee OA, which is thoroughly described in previous studies (23, 28).

Statistical analysis

We will develop a specific statistical analysis plan for each specific sub-study that will be conducted to answer the aforementioned research questions.

To describe the sample, we will use means and standard deviations (SDs), frequencies and percentages. These will follow several general principles. We will aim for the inclusion of all available patients to limit potential selection bias. In the statistical modelling we will aim for

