estimation of causal effects and statistical models will be chosen accordingly using direct acyclic graphs (DAGs) to enable proper confounding control. For confounding control, we will use regression models or inverse probability weighting. For analysis of panel data (i.e. longitudinal repeated measurements of the participants and/or data clustered by caregiver) we will use conditional or marginal models. For time-to-event data we will use the Cox regression model, or, if appropriate, a parametric version. For mediation analysis, we will use linear models or maximum likelihood structural equation models when appropriate. For categorical outcomes we will use other approaches such as logit and probit models. We will report the results from all analyses as relevant estimated effect size (such as risk differences, risk ratios or hazard ratios) with 95% confidence intervals and interpret these for clinical relevance, irrespectively of statistical significance.

Power calculation

Power analysis revealed that for the initial short-term follow-up, a sample size of 70 participants will be enough to identify a minimally clinical important change of 1.5 units in pain with a calculated mean pain of 5.2 (sd 2.2) at start, power of 80%, $p<0.05$.

For the other studies, we will not perform any power calculation. This is because the question of power can be considered secondary in such a setting where the sample size is driven by data availability and not decided a priori. Therefore, we will include all the available data from the start.

Ethical considerations

Storage and management of data

The data set will be stored in a database at Arthro Therapeutics head office in Malmö. The platform is designed to securely store, manage and analyse data in accordance with the European Union general data protection regulation (GDPR). The process of linkage, storage and management of data, the role of informed consent in register-based research and safeguarding the integrity of study participants follows the legal and ethical frameworks as described by Swedish law and ethical boards. This has been described by Ludvigsson et al (30).

Data sharing

All information regarding individual patients is subject to confidentiality in accordance with The Public Access to Information and Secrecy Act (SFS 2009:400) chapter 25 article 1. Therefore, no unauthorised person will have access to data.

Significance

Preliminary results

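### Should participants who report arthritis such as RA at sign-up be left out of the primary hand-OA estimate?

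*Combined protocol and SAP*

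**What the plan says.** Under Purpose and goal, the study evaluates change during a programme "containing exercise and education for patients with osteoarthritis (OA) of the hand". The primary outcomes are pain (0-10 NRS) and hand function (FIHOA) after 3 months. The Project description calls the study observational and registry-based, and no comparison group is described.

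On who is analysed, the Statistical analysis section gives one general principle: "We will aim for the inclusion of all available patients to limit potential selection bias". It also announces "We will develop a specific statistical analysis plan for each specific sub-study" and adds, without naming variables, "For confounding control, we will use regression models or inverse probability weighting".

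On diagnosis, the section on the digital program says "A majority of included participants had a clinical diagnosis of hand arthritis from a PT, OT or physician". The same sentence adds that every participant had seen a healthcare provider in person about their hand OA before joining. The next one reads "The clinical diagnosis of OA was confirmed by a PT or OT via telephone", with referral to face-to-face care before inclusion where that was judged necessary.

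Table 1 lists "If has arthritis (e.g RA" at sign-up, among lung disease, diabetes, cardiovascular disease and balance problems. It also lists diagnostic and red-flag questions, pain medication and its changes, and a free-text medical field.

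**The concern.** The question is about hand OA, and function is scored with an index built for hand OA. The database nevertheless expects some participants to report RA-type arthritis, and the only population rule is to include everyone. Inflammatory arthritis can affect the same joints and both primary outcomes. Its course depends on treatments that Table 1 does not record in a structured way, since its medication items concern pain medication.

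With no control group, any other cause of change in hand pain goes straight into the estimate, and the plan says it aims for causal effects. The entry wording seems to add to the doubt: only a majority had a prior clinical diagnosis, it is called hand arthritis rather than OA, and confirmation was by telephone.

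If flagged participants change differently, the pooled mean is shifted and the claim that it describes hand OA is weaker. The apparent remedy costs little: restrict the primary set to those who answered no, using a variable already collected.

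**Working it through.** **Who the flagged participants are.** Three safeguards apply before inclusion: an in-person visit about hand OA for everyone, confirmation of OA by a physiotherapist or occupational therapist, and face-to-face referral where needed. Diagnostic and red-flag questions are also asked. None of these rules out co-existing RA, but together they make a flagged person more likely an OA patient with a comorbidity than a misdiagnosed one. The item's place in a list of comorbidities fits that reading.

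**Inputs from the Power calculation section.** 70 participants, a change of 1.5 units, baseline mean 5.2 (SD 2.2), power 80%, alpha 0.05 (two-sided assumed). The SD of change is not given.

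**The plan's own figure.** A two-group normal formula gives 2 × 2.2² × (1.960 + 0.842)² / 1.5² = 33.8, so 34 per group and 68 in total. The t version gives 34.75, so 35 per group and 70 in total. The figure of 70 thus matches a two-group formula. For within-participant change, a paired t test with SD 2.2 at both times needs 36 participants at correlation 0 and 19 at correlation 0.5, so 70 is ample.

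**Shift from pooling.** Let f be the flagged share and d the difference in mean change between flagged and unflagged participants. The pooled mean differs from the unflagged mean by f × d. Both are assumptions:

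| f | d = 0.5 | d = 1.0 | d = 1.5 |
|---|---|---|---|
| 2% | 0.010 | 0.020 | 0.030 |
| 5% | 0.025 | 0.050 | 0.075 |
| 10% | 0.050 | 0.100 | 0.150 |
| 20% | 0.100 | 0.200 | 0.300 |

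For shares of 3-10% and differences of 1.0-1.5, the range is 0.03 × 1.0 = 0.03 to 0.10 × 1.5 = 0.15 points. Against the 1.5-unit target that is 2% to 10%. The extreme cell, 0.30, is 20%.

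**Against sampling error.** With an assumed SD of change of 2.2 (equal SDs, correlation 0.5), the standard error at 70 is 2.2/√70 = 0.263. The shift is then 0.03/0.263 = 0.11 to 0.15/0.263 = 0.57 standard errors.

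**What it would take to matter.** To move the mean by half the target, 0.75 units, with 10% flagged, d would have to be 0.75/0.10 = 7.5 points, more than the whole baseline mean of 5.2. With 20% flagged it would have to be 0.75/0.20 = 3.75 points.

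**FIHOA.** The documents give no target or SD, so only the proportion can be stated: a 10% share passes on one tenth of whatever difference exists.

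**Cost of excluding flagged participants.** If 20% were removed, 56 remain. Paired power for 1.5 units is 94% at correlation 0 and 99.9% at correlation 0.5. Lost precision is therefore not the argument against exclusion for a within-participant analysis. On the two-group formula that the figure of 70 matches, power would fall to 72%, but no second group is described.

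**The case for a change.** The strongest case for a change is that the plan is silent, the flag exists, and silence leaves the analysis set to be chosen after the data are seen. Confirming OA does not exclude co-existing RA. Use of the flag for screening is possible but not stated. The provision for a later SAP and the general text on confounding control leave the point open rather than settle it. One sentence and one filter would settle it at almost no cost. Also, because all available patients are included, the sample may exceed 70. With four times as many participants the standard error halves to 0.13, and a shift of 0.15 would be 0.15/0.13 = 1.15 standard errors.

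The silence is real, and so is the small risk of a post-hoc choice. The rest carries less weight. A larger sample makes a fixed shift more visible statistically but no larger clinically: it is still at most 10% of the target under the assumptions above. Nor is it established that treatment for inflammatory disease is beyond later adjustment, since Table 1 has a free-text medical field and the outcomes section lists changes in medications without limiting them to analgesics. That capture is unsystematic, but it is not nothing.

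The filter also has a cost of its own. The item is self-entered and is limited neither to the hand nor to inflammatory disease. The protocol itself describes these OA patients as having hand arthritis, so a participant with OA alone could reasonably answer yes. Making 'no' the entry condition for the primary set could discard genuine cases, against the plan's stated reason for broad inclusion. It would not make the result causal either, because the remaining participants would still have no comparison group.

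**Conclusion.** No change to the plan follows. Part of this is a gap that analysts can fill sensibly, and part is a fair trade-off between a broad population and a narrower one defined by an imprecise self-report item. People with confirmed hand OA and another condition fall within the stated population, and the plan gives a reason for keeping them.

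The assumed shift of 0.03-0.15 NRS points, direction unknown, is 2-10% of the 1.5-unit target and roughly 0.1-0.6 standard errors at 70 participants. It would not overturn a conclusion about a clinically relevant change. This rests on a flagged share of 3-10%, a difference of 1.0-1.5 points and an SD of change of 2.2, none of which the documents give. At a 20% share with a 1.5-point difference the shift would be 0.30, large enough to mention in the report but still one fifth of the target.

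The usual practice is enough: keep all available patients as the primary set, report how many answered yes, and show 3-month pain and FIHOA change with and without them. The promised sub-study SAP is the natural place for that.
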